8.2 Plan modification

8.3 Informed consent

8.4 Confidentiality

1. ABSTRACT

Basic information on clinical practice of medical devices:

Device Classification: Class II medical devices

Specification Model: RS-200-1A

Date: September 20, 2020

Sponsor: Zuoguan Medical Devices Co., Ltd. at Suzhou Industrial Park

Practice Title

A Randomized, Controlled, Multi-centre Clinical Study on the Effectiveness and Safety of repeated low-level red-light (RLRL) for myopia control in children and adolescents with high myopia

Practice Purpose

A Study on assessing the effectiveness and safety of RLRL for myopia control in children and adolescents with high myopia.

Subject Population

Subject: Children aged 6-16 with at least one eye with myopia of cycloplegic spherical equivalent refraction (SER) at least -4.0 D

Sample size: 192 subjects are planned to be enrolled and assigned to the intervention group or control group according to a ratio of 1:1

Practice Design

Overall design:

This prospective, single-blind, parallel-group, multi-center randomized clinical trial was conducted at six tertiary hospitals. Participants between 6 and 16 years old with at least one eye with a spherical equivalent refraction (SER) of -4.0 D or greater were recruited. The enrolled participants were randomly placed at a 1:1 ratio into

intervention (RLRL treatment plus single-vision spectacles) or control (single-vision spectacles) groups. The participants attended follow-up appointments 1, 3, 6, 9, and 12 months after the baseline evaluation.

Outcomes:

1. Primary Outcome: Change of Axial length (AL, mm) at 12-month follow-up
2. Secondary Outcome: Change of cycloplegic spherical equivalent (SE, D) at 12-month follow-up
3. Optional Indicators:

Changes of uncorrected visual acuity (UCVA), best-corrected visual acuity (BCVA), intraocular pressure, etc.;

Changes of corneal thickness (CT), anterior chamber depth (ACD) and lens thickness (LT);

Observe macula and the structure of fundus around the optic disc;

Observe the choroid/retinal thickness of the fundus;

Compliance index: frequency of equipment uses.

Safety assessment

- ① Sudden vision loss;
- ② Afterimage time over 5 minutes;
- ③ Side effects such as glare, photophobia and flickering;
- ④ Structural damage to retina: tissue disruption or discontinuity, edema, or other abnormalities in the photosensory layer of the SS-OCT images;
- ⑤ Increased intraocular pressure etc.

Participants selection and exclusion criteria:

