3.1 Eligibility criteria

Inclusion criteria

- ① Age 6-16 years old, no gender limit;
- ② Either eye meets the diagnosis of myopic refractive error and the myopia of cycloplegic spherical equivalent refraction (SER) at least -4.0 D, astigmatism 2.0 D or less, anisometropia 3.0 D or less, and best-corrected visual acuity (BCVA) of LogMAR 0.2 or better.
- ③ Have normal thinking and language communication skills, and be able to actively cooperate with the required treatment;
- ④ No contraindications to the treatment of atropine such as acute ocular inflammation, dry eye, keratoconus, diabetes, etc.;
- ⑤ Written informed consent of the guardian and the child.

Exclusion criteria

- ① A history of photosensitivity, glaucoma, glaucoma syndrome, ocular hypertension, and macular pathology or damage in the fundus;
- ② Corneal curvature examination, the average K value of the anterior surface of the cornea is ≥ 45 ;
- ③ Patients with heart, liver, kidney and other systemic diseases and congenital hereditary myopia;
- ④ Patients with chronic eye diseases such as ocular trauma and oblique or surgical eyes, atopic keratoconjunctivitis;
- ⑤ Patients with previous eye diseases such as inverted trichiasis, severe corneal and conjunctival infections;
- ⑥ Patients with neurological diseases and allergies or contraindications to atropine drugs or other therapeutic drugs;
- ⑦ Patients with immune system and systemic diseases such as albinism, psoriasis, nephrotic syndrome, systemic lupus erythematosus, diabetes, etc.;
- ⑧ People with epilepsy, mental disorders and unable to communicate normally;

- ⑨ Those who have previously received other treatments to control the development of myopia, such as the use of anticholinergic drugs such as atropine within 3 months, or participated in other functional frame mirrors, multifocal soft mirrors and other related researchers;
- ⑩ Other situations that the researcher judges are not suitable for participating in the research.

Participant withdrawal or termination

A study investigator will terminate participation in the study for the following reasons:

- 1) The patient receives other myopia control treatments;
- 2) Patients continuously stop using Eyerising equipment for more than 14 days;
- 3) Severe comorbidities or adverse events: patients cannot tolerate light, have obvious eye allergies such as tearing, skin rash, and the after-image time after low-energy laser treatment exceeds 5 minutes;

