- 4) Serious safety problems occurred repeatedly during the test (such as serious adverse events related to the test);
- 5) China Food and Drug Administration ordered the suspension of the test for some reason;
- 6) Sponsor requests suspension (such as funding reasons, management reasons, etc.).

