7) Slit-lamp examination: Slit-lamp examination will be used to examine the anterior segment, lens, vitreous, and fundus, and any abnormalities will be recorded.

8) Optical coherence tomography (optional): SS-OCT fundus image acquisition and data processing: using swept source OCT (DRI OCT-1 Atlantis, Topcon) 9 Line Radial follow-up mode to scan and collect images to obtain fundus pictures and fundus tissue tomographic images. Before the collection, the subjects should be asked to sit still for a while, avoid taking coffee and drinks; during collection, doctors should pay attention to correct the axial magnification; researchers should concentrate on collection time to avoid the influence of the time rhythm fluctuation of choroidal thickness. After the choroidal boundary is automatically segmented by the machine's built-in software,

manual verification and correction are carried out, and the choroidal thickness data of 9 regions of the fovea and the inner, middle and outer rings (upper, lower, nasal, and temporal) are obtained.

2. Follow-up Examinations:

- 1) Questionnaire: A questionnaire on adverse events following the intervention will be administered at each follow-up visit and unexpected visits for children in the intervention group. Children and their parents/guardians will be asked about the side effects, including but not limited to short-term glare, flash blindness, and afterimages.
- 2) Visual acuity: An ETDRS chart (Guangzhou Xieyi Weishikang, Guangzhou, China) with standard illumination will be used to measure distance visual acuity. Visual acuity measurement is performed at a distance of 4 meters. Uncorrected visual acuity will be measured for each follow-up visit, best corrected visual acuity will be measured for the baseline, 6-month and 12-month follow-up visit.
- 3) Ocular biometric measurements via IOLMaster: IOLMaster will be used to measure the axial length of both eyes. Five measurements will be taken for each eye. The axial length measurement will be based on the mean of these five values if the desired precision (<0.05 mm) is achieved.
- 4) Cycloplegia: Cycloplegia will be induced with three drops of 1% cyclopentolate administered at the 0, 5th, and 20th minute to each eye. The light reflex and pupil dilation will be checked after an additional 15 minutes. Dilation and light reflex status will be recorded and full cycloplegia will be justified if the pupil dilates to 6 mm or greater and the light reflex is absent.

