- 5) Cycloplegic auto-refraction: Cycloplegic auto-refraction will be conducted using an auto-refractor (KR-8800, Topcon, Tokyo, Japan). The same auto-refractor will be used throughout the study. It will be calibrated before each examination session to ensure there is no equipment drift during the long follow-up process.
- 6) Slit-lamp examination: Slit-lamp examination will be used to examine the anterior segment, lens, vitreous, and fundus, and any abnormalities will be recorded.

7) Optical coherence tomography (optional): Swept Source-OCT (DRI OCT-1 Atlantis, Topcon) will be used to capture the macular scan. Shooting mode: 12 mm radial scan mode (follow up mode).

8) Safety assessment

- ① The incidence of allergic reactions;
- ② Afterimage duration exceeds 5 minutes;
- ③ Decreased near visual acuity;
- ④ Levels of side effects such as photophobia and blurred vision;
- ⑤ Increased intraocular pressure, headache, nausea and vomiting, etc.

Follow-up Schedule

(1) Visit 1: Screening period (-7~0 days)

- 1) Sign the "Informed Consent";
- 2) Record the general information of the patient;
- 3) Record the medical history;
- 4) Perform visual inspection, axial inspection, intraocular pressure inspection, equivalent spherical lens measurement, slit lamp inspection, OCT inspection;
- 5) Review the inclusion and exclusion criteria;
- 6) Record the combined/concomitant medication;

(2) Visit 2: Enrolment and randomization (day 0)

- 1) Randomly group, and the intervention group will receive experimental devices;
- 2) Record device defects;
- 3) Record the combined/concomitant medication;

(3) Visit 3: Day 30±14

- 1) Perform visual inspection, axial inspection, and intraocular pressure inspection;
- 2) Record the combined/concomitant medication;
- 3) Record adverse events/device defects.

(4) Visit 4: Day 90±14

- 1) Perform visual inspection, axial inspection, and intraocular pressure inspection;

2) Record the combined/concomitant medication;

3) Record adverse events/device defects.

(5) Visit 5: Day 180±14

1) Perform vision examination, axial examination, intraocular pressure examination, equivalent spherical lens, slit lamp examination, and OCT;

2) Record the combined/concomitant medication;

3) Record adverse events/device defects.

(6) Visit 6: Day 270±14

1) Perform visual inspection, axial inspection, and intraocular pressure inspection;

2) Record the combined/concomitant medication;

3) Record adverse events/device defects.

(7) Visit 7: Day 365±14

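### The only harm-based criterion above the individual child requires repeated serious problems, so a first serious eye injury prompts no stated review; the safety lists and OCT wording also disagree

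*Combined protocol and SAP*

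**What the plan says.** **Stopping criteria (Section 3.1, Participant withdrawal or termination).** Items 1 to 3 concern one child. Item 2 is "Patients continuously stop using Eyerising equipment for more than 14 days". Item 3 opens "Severe comorbidities or adverse events: patients cannot tolerate light, have obvious eye allergies such as tearing, skin rash" and adds a prolonged afterimage; its examples do not name vision loss or retinal injury. Items 4 to 6 describe trial-level situations. Item 4 is "Serious safety problems occurred repeatedly during the test (such as serious adverse events related to the test", with no count, named event, decision maker or action. Item 5 is a regulator's order with no reason specified. Item 6 is a sponsor's request, with funding and management as its examples.

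**Safety outcomes.** The abstract's safety assessment includes "Sudden vision loss" and "Structural damage to retina: tissue disruption or discontinuity, edema, or other abnormalities in the photosensory layer of the SS-OCT images". The follow-up safety list in Section 4.2 (item 8) names neither. It does include "Decreased near visual acuity", but the schedule of events in Section 4.3 contains only distance vision.

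**OCT.** Item 7 of the follow-up examinations reads "Optical coherence tomography (optional): Swept Source-OCT (DRI OCT-1 Atlantis, Topcon) will be used to capture the macular scan". The visit schedule and the table in Section 4.3 list OCT at screening, day 180 and day 365 without that qualifier. Section 5.2 has six ophthalmologists, one per centre, read the scans, but gives no timing or escalation.

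**Questionnaire.** The adverse-event questionnaire in Section 4.2 is given "at each follow-up visit and unexpected visits for children in the intervention group".

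**The concern.** Safety is half of the stated purpose. The device is a Class 3R laser that children view twice a day for 12 months. The abstract identifies the two harms that matter most for such a device, but no action above the affected child is attached to a first occurrence of either. Followed as written, one centre could manage a first related retinal injury locally while up to 95 other treated children (96 − 1) across six centres carried on, with no required point at which anyone decides whether they should.

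The inconsistent safety text adds to this. A centre working from the Section 4.2 headings could skip the scan on which the abstract's definition of retinal damage depends. Symptoms elicited by questionnaire would have no comparison from the control arm.

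**Working it through.** **1. Does any other provision require a trial-level review after a first event?**

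| Provision | What it does | Requires a review for the other children? |
|---|---|---|
| Section 3.1, item 3 | Can end the affected child's participation | No |
| Section 3.1, item 4 | Applies once serious problems have recurred | Not at a first event |
| Section 3.1, items 5 and 6 | Regulator or sponsor may suspend | No; neither is tied to harm |
| Section 6, Monitoring | Links duration of surveillance to serious adverse events; checks adverse-event management and documentation | No |
| Section 8, Plan modification | Allows changes for immediate hazards without prior approval | No; permits, sets no trigger |
| Device appendix | Fundus retinopathy is a contraindication, and use must follow the instructions | No; concerns one child |
| Section 5.2 | Ophthalmologists read OCT scans | No timing or escalation |

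The lead-in to the six items speaks of ending participation. If item 4 is therefore read at child level, no harm-driven trial-level criterion is stated at all.

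**2. Which ascertainment gaps are real?**

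- Both arms are scheduled for distance acuity and adverse-event recording at every follow-up visit, and for slit-lamp examination (including fundus) and OCT at days 180 and 365.
- Only the questionnaire is restricted to one arm, so only solicited symptoms lack a control comparison.
- Near acuity is listed as a safety item but no near test is scheduled.
- The OCT heading and the OCT schedule conflict.

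**3. Number exposed.** Section 3.6 gives difference 0.20 mm, SD 0.40 mm, α 0.05 (two-sided assumed), power 90% and 10% loss. The normal approximation, n = 2(1.960 + 1.282)² × 0.40² / 0.20², gives 85 per arm. The t-test solution is 85.03, rounded up to 86, as stated. Then 86 / 0.90 = 95.6, rounded up to 96 per arm and 192 in total. The plan's figures reproduce, and 96 children are exposed to the device.

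**4. How often would a first event be the only one?** Event risk p is assumed, because the documents give none. *Repeatedly* is taken at its loosest, as two or more events across the trial. With X ~ Binomial(96, p):

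- P(X ≥ 1) = 1 − (1 − p)^96
- P(X = 1) = 96 p (1 − p)^95
- P(X ≥ 2) = P(X ≥ 1) − P(X = 1)

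| p | P(X ≥ 1) | P(X ≥ 2) | P(X = 1) | P(X = 1) / P(X ≥ 1) |
|---|---|---|---|---|
| 0.1% | 9.2% | 0.4% | 8.7% | 95% |
| 1% | 61.9% | 24.9% | 37.0% | 60% |
| 2% | 85.6% | 57.5% | 28.2% | 33% |
| 5% | 99.3% | 95.6% | 3.7% | 4% |

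The absolute gap, P(X = 1), is greatest at p = 1/96, about 1%, and shrinks on either side. Only the last column keeps rising as events become rarer.

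**The case against.** The strongest reply is that item 4 is a termination criterion, not a review trigger, and that requiring repetition before ending participation is a defensible choice. That stands: item 4 should be kept, and the table above compares reaching a first-event review with reaching a repeated-event termination, which are different actions. But the plan has no separate review trigger, so item 4 is the only harm-based threshold a reader can find above the child.

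A second reply is that the plan leaves many routes open: item 3, the contraindications, sponsor or regulator suspension, the immediate-hazard clause in Section 8, and GCP. This also stands as far as it goes. These routes allow a response; none of them obliges anyone to consider the other treated children.

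Several stronger readings are tempting and are not supported:

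- *An injured child would have to stay on the device.* Item 3's general heading and the contraindications allow that child to be stopped.
- *The two harms would go unrecorded.* Acuity, slit-lamp and adverse-event recording would capture much of them. The Section 4.2 list includes blurred vision and is open-ended, and the questionnaire is not limited to its examples.
- *There is no control comparison for safety.* This is true only of solicited symptoms.
- *Follow-up OCT is simply optional.* The schedule lists it at two follow-up visits, so the text is inconsistent.
- *The gap keeps growing as events get rarer.* In absolute terms it peaks near a 1% risk.

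The figure of 95 other children is a ceiling. It assumes all are enrolled and still on treatment, and the day 365 scan comes as that child's treatment ends. Sections 2.1 and 2.2 are not in the available text and might name a responsible role, but that would not change item 4's wording.

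**Conclusion.** The point holds as a gap in what the plan requires, not as an absence of any stop or record. A first device-related sudden vision loss or retinal structural injury prompts no stated review of whether the other treated children should continue. The safety list, OCT heading and questionnaire are inconsistent with the abstract, with the schedule and between arms.

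This conclusion rests on reading the text and does not depend on the assumed risks. The size is illustrative only: about a 9%, 37%, 28% or 4% chance that a trial has exactly one such event, at risks of 0.1%, 1%, 2% or 5%. It assumes independent events in all 96 treated children and the loosest reading of item 4. The change is inexpensive and should be made.

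**What to change.** 1. **Keep item 4 and add a sentence beside it.** Any single sudden vision loss, or new photosensory-layer structural damage on OCT, in a treated child pauses that child's device use. It also prompts a documented review by the sponsor and the main-centre investigator, with notice to the ethics committee, on whether enrolment and treatment continue. State that such a hold is neither an item 2 withdrawal nor a censoring event under Section 5.2, and that axial length visits continue.
2. **Align Section 4.2.** Use the abstract's safety list, delete the word optional from the follow-up OCT so that the day 180 and day 365 scans are required, and give the adverse-event questionnaire in both arms.
3. **Read scans promptly.** Have the existing masked ophthalmologists read the day 180 and day 365 scans soon after acquisition. The main-centre investigator who holds the envelopes can look up the arm, so readers stay masked.

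**Cost.** No new committee or visit is needed. Costs are a protocol amendment, earlier OCT reading, any scans that centres would otherwise have skipped, and a short questionnaire for controls.

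Some holds will follow unrelated findings. At assumed rates of 0.5%, 1% and 3%, 96 × rate gives 0.5, 1.0 and 2.9 expected, and 1 − (1 − rate)^96 gives a 38%, 62% and 95% chance of at least one. A 14-day hold costs 14 × 2 = 28 of 365 × 2 = 730 sessions (3.8%) for that child.

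With the exemption, a hold loses no axial length data. Without it, losing three of 86 intervention-arm completers would lower power for 0.20 mm (SD 0.40 mm, two-sided t-test) from 90.3% to 89.8%.

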3.2 Recruitment and informed consent

Children who met the Inclusion criteria and their parents or guardians will be invited to participate in the study at the refractive clinic and optometry center of the research hospital through poster advertisements and physician referrals. Prior to collecting baseline data, written informed consent will be obtained from the parents/guardians of all participants.

3.3 Randomization and masking

A statistician without contacts with the participants generated the randomization sequence using SAS software (version 9.4; Cary, NC, USA). All eligible participants were randomly assigned to the intervention (RLRL plus SVS) or control (SVS only) groups at a 1:1 ratio. The randomization process adopted central stratification block randomization with block sizes of four or six. Each eligible participant was assigned a number based on their study entry sequence. Random assignment outcomes were

recorded in sealed envelopes with the corresponding sequential numbers written on the covers. Then, an investigator at the main center took custody of the envelopes. Each time an eligible participant's informed consent was acquired, the investigators responsible for group allocation at the six centers contacted the investigator holding the envelopes by telephone. The investigator immediately opened the envelopes and provided information on the group allocation of the newly enrolled participants. Owing to the nature of the intervention, the participants were aware of their assigned treatment groups. However, outcome assessors, including clinical examination technicians, optometrists, ophthalmologists, and statisticians, were blinded to the treatment allocation.

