3. STUDY DESIGN

This trial is a randomized, controlled, multi-centre clinical trial. The subjects selected 192 children aged 6-16 who had developed high myopia, and divided them into intervention group and control group with 96 cases each. The intervention group was treated with the Eyerising RLRL and single vision spectacle lenses, and the control group was treated with single vision spectacle lenses. Then, we compare the changes of myopia during the observation period between the two groups, and evaluate the safety and effectiveness of the test device.

Subjects will be screened after signing the informed consent form (as early as 7 days before the randomization day). The screening test can use the results of the ophthalmological examination in hospital within 1 week, and subjects enter the group after confirming that they meet the selection conditions. On the day of enrolment, the group is confirmed after consultation with the parents, and determine whether to receive

equipment for treatment based on the results of the grouping. Visits were conducted 30±14 days, 90±14 days, 180±14 days, 270±14 days, and 365±14 days after enrolment.

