5.2 Statistical analysis plan

The intention-to-treat (ITT) population comprised participants randomly assigned to either group. Data from all participants who attended at least one subsequent follow-up visit were included in the analysis, regardless of treatment or follow-up visit compliance. No imputation was used for the missing data. Individuals who switched to other myopia treatment modalities, such as orthokeratology or atropine eye drops, or discontinued the RLRL treatment, were censored. If a participant had only one eye with a SER exceeding -4.0 D, that eye was selected for the statistical analysis. In cases where both eyes were exceeding -4.0 D, the right eye was chosen for the analysis.

Treatment efficacy was assessed using longitudinal mixed models for primary (changes in AL) and secondary (changes in SER and IOP) outcomes at multiple follow-up visits. The mixed effects model was fitted with a random intercept and random slope for the participant, where the group, visit, group-by-visit interaction, baseline age, sex, and baseline AL were fixed effects. Estimated mean treatment differences and corresponding 95% confidence intervals (CIs) were derived from mixed models. UCVA alterations were classified into three categories: decline by two or more lines, stable (within a line), or improvement by two or more lines. The BCVA at the 12-month and baseline was evaluated against the 20/25 standard.

Sensitivity analyses were conducted to assess the treatment effects of therapy in controlling myopia progression, specifically axial elongation and SER progression, across different baseline SER and age groups.

A longitudinal mixed-model analysis was conducted to assess the relationship between treatment efficacy and compliance within the intervention group. Treatment compliance in the intervention group was measured as a percentage of the total number of assigned treatment sessions.

Safety analyses were performed in the ITT population. All adverse events were reported individually. Six ophthalmologists, one from each center, independently scrutinized the OCT scans for potential structural anomalies.

6.MONITORING

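### Randomisation is described as stratified, but the primary axial-length model has no centre or stratum term; if centre was the factor, the planned 95% CI is slightly too wide

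*Combined protocol and SAP*

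**What the plan says.** On allocation, section 3.3 states: "The randomization process adopted central stratification block randomization with block sizes of four or six". No stratification factor is named there or elsewhere. The Abstract describes the setting: "multi-center randomized clinical trial was conducted at six tertiary hospitals".

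The mechanics in section 3.3 are brief. "Each eligible participant was assigned a number based on their study entry sequence"; assignments were "recorded in sealed envelopes with the corresponding sequential numbers written on the covers"; and "an investigator at the main center took custody of the envelopes", opening them when any of the six centres telephoned. The text does not mention a list, number series or envelope set for each stratum. Nor does it say that there was only one series.

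The only balance given in figures is overall: 1:1 in section 3.3, and section 3 says that the trial "divided them into intervention group and control group with 96 cases each".

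On analysis, section 5.2 specifies a mixed model with a random intercept and slope for the participant, "where the group, visit, group-by-visit interaction, baseline age, sex, and baseline AL were fixed effects". The treatment differences and 95% CIs come from this model. Centre or stratum appears neither in section 5.2 nor in the Abstract's summary of the analysis.

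**The concern.** When allocation is balanced within strata, differences between strata largely cancel out of the treatment comparison. A model that omits the strata does not know this. It counts the between-stratum variation as error, so the standard error is larger than the design warrants. The participant random effects do not help: they place centre variation in the between-participant variance, which is the variance that drives the standard error of the group contrast.

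What is at stake is precision. The primary CI would be wider than necessary, the test would run below its nominal level, and some power would be lost, although centre is already known for every child. A smaller issue is that a reader cannot tell from section 3.3 what was stratified or how, and so cannot check that the model matches the design.

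**Working it through.** **Inputs from the documents.** Section 3.6: α 0.05, power 90%, SD 0.40 mm, difference 0.20 mm, 10% loss. Section 3.3: blocks of 4 or 6, 1:1. Abstract: six centres, five follow-up visits.

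**Assumptions.** The documents give no between-centre variance, so an ICC from 0 to 0.20 for 12-month AL change is assumed. Centre sizes are also not given; equal centres are used, with 40/20/15/10/10/5% as a check.

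**Step 1: the plan's own figure.** n per group = 2 × SD² × (z₀.₉₇₅ + z₀.₉₀)² / Δ² = 2 × 0.16 × (1.960 + 1.282)² / 0.04 = 84.1, so 85. The exact t calculation gives 86 (power 90.3%). 2 × 86 = 172, and 172 / 0.9 = 191.1, so 192. The stated 86, 172 and 192 reproduce with a two-sided test.

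**Step 2: baseline precision.** SE = √(2 × 0.16 / 86) = 0.0610 mm. CI width = 2 × 1.974 × 0.0610 = 0.241 mm.

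**Step 3: expected effect of omitting centre.** Let ICC be the share of the variance that lies between centres. With blocks inside each centre, the arm difference varies essentially through the within-centre share, 1 − ICC. The residual of a model without centre also contains the between-centre share; with six centres it picks up about 5/6 of it. Hence:

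width ratio ≈ √(1 + (5/6) × ICC / (1 − ICC)) = 1.022, 1.045 and 1.099 for ICC 0.05, 0.10 and 0.20.

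type I error ≈ 2Φ(−1.96 × ratio) = 4.5%, 4.0% and 3.1%.

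**Step 4: simulation.** 172 completers in six equal centres, blocks of 4 or 6 within centre, a linear model of 12-month change with and without centre, and 3,000 to 4,000 runs per scenario. This simplifies the mixed model to one time point.

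| ICC (assumed) | CI width without → with centre (mm) | Ratio | Type I error without centre | Power without → with centre | Difference (points) |
|---|---|---|---|---|---|
| 0.05 | 0.2394 → 0.2345 | 1.021 | 4.5% | 90.55% → 91.23% | 0.68 |
| 0.10 | 0.2383 → 0.2283 | 1.044 | 4.0% | 91.35% → 92.47% | 1.12 |
| 0.20 | 0.2363 → 0.2153 | 1.098 | 3.4% | 92.90% → 95.25% | 2.35 |

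The simulated ratios agree with step 3. With 4,000 runs, the simulation error of a 5% rate is √(0.05 × 0.95 / 4000) = 0.34 points, so at ICC 0.05 the type I shortfall rests as much on step 3 as on the simulation. Coverage of the planned CI is about 95.5%, 96.1% and 96.6%, against about 95% with centre in the model. With the unequal centres and ICC 0.20, type I error is 2.9% and coverage 97.1%.

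**Step 5: if there was one trial-wide series instead.** For 192 children, the overall arm difference is at most 2. The largest difference in any one centre averages about 8 (95th percentile 13), against 1.6 (95th percentile 3) with blocks per centre. Type I error of the planned model stays between 4.45% and 5.48% over all ICC and centre-size scenarios, which is nominal within simulation error.

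**The case against.** Several points on the other side have force.

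- **The factor is not named.** The word central may mean that randomisation was run centrally. If the factor were, say, age, the model already has an age term and centre would not be the matching addition. This stands, and it makes the size conditional. It does not remove the gap, because the plan should say what was stratified and carry that factor into the model.
- **The effect is small and in the safe direction.** This stands. Simulated power without centre is above the planned 90% in every row of the table, and false positives become rarer. Age, sex and baseline AL may also absorb some centre variation, which the calculation ignores.
- **The model grows.** With visit categorical, centre adds 5 parameters and centre-by-visit 5 × 4 = 20, so 25 in all. This is a real cost, but one that about 172 children with repeated visits can support.

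A reader might go further and infer from the numbering rule that all six centres drew on one series, so that nothing was stratified and the stated balance was not delivered. The documents do not support this. Numbering by order of entry also fits separate centre series held by one custodian, and the sentence shortly before it claims stratified blocks. The only balance given in figures is 1:1 overall, and one blocked series holds that to within 2 children. Only within-centre balance would be lost, and the planned model would keep valid error.

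**Conclusion.** The point holds as a mismatch between the stated design and the primary model: stratified randomisation is claimed, and no centre or stratum term is in the analysis. If centre was the factor, the planned CI is about 2%, 4% or 10% too wide and the power loss about 0.7, 1.1 or 2.4 points, at an assumed ICC of 0.05, 0.10 or 0.20. The result rests on that assumed range, on reading the stratification as by centre, and on a single-time-point simplification of the mixed model.

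It is an avoidable loss of precision, not a threat to validity: the type I error is not inflated and the sample size needs no change. That section 3.3 does not show how stratified blocks were carried out is a secondary reporting gap.

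**What to change.** **Section 5.2.** Add centre, and any other stratification factor used, as a fixed effect in the primary AL model, together with its interaction with visit. The interaction is needed because the endpoint is change at 12 months: a main effect alone imposes the same centre shift at every visit, so the adjustment would not fully reach that contrast.

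**Section 3.3.** Name the stratification factor or factors, and state whether block lists, participant numbers and envelope series are separate for each stratum. Parts of the text are in the past tense; if allocation is complete, this is a clarification of what was done.

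**Cost.** A few lines of text and up to 25 parameters. If centres do not differ at all (ICC 0), adding centre in the simulation changes the mean CI width from 0.2402 to 0.2404 mm under centre-stratified blocks, and from 0.2405 to 0.2441 mm (1.5%) under one trial-wide series. No extra children or data are needed.
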